Cut down, Annoyed, Guilty, and Eye-opener (CAGE).....	19
PTSD Checklist – short version (PCL-5).....	19
Data and Safety Monitoring (DSM) Plan.....	20
Monitoring Entity, Roles and Responsibilities	20
Roles of the SMC	20
Responsibilities of the SMC.....	20
Meetings of the SMC	21
Procedures for monitoring study safety, minimizing research-associated risk and protecting confidentiality of participant data	21
Procedures for Identifying, Reviewing, and Reporting Unanticipated Events	22
Compliance across Sites.....	23
Study Completion and Closeout Procedures	25

PRÉCIS

Short Title: Preoperative Pain and Rehab Education (PrePARE)

Objectives

[figure not shown]
Using a multi-site, double-blind, two-arm, parallel, randomized controlled trial with Veterans at-risk for PPSP post-TKA, the following aims will be addressed:

1. Primary Aim: To examine the superior efficacy of ACT versus Attention Control (AC) on postoperative pain intensity and functioning in at-risk Veterans undergoing TKA. Changes in pain intensity and functioning from baseline to 6 weeks, 3 months and 6 months post-TKA will be compared. Level of pain intensity will be measured using the BPI Pain Severity Subscale and level of functioning will be measured using the KOOS Activities of Daily Living and Quality Of Life Subscales.
2. Secondary Aims: A) To examine the superior efficacy of ACT versus AC on the severity of anxiety and depressive symptoms and improvements in coping skills. Changes from baseline to 6 weeks, 3 months and 6 months post-TKA will be compared. Anxiety and depressive symptoms will be measured with the Depression, Anxiety and Stress Scale (DASS-21). Coping skills (i.e. Pain Acceptance and Engagement in Values-Based Behavior) will be measured with the Chronic Pain Acceptance Questionnaire and the Chronic Pain Values Inventory. B) To evaluate whether decreases in distress-based symptoms and increases in coping skills mediate changes in pain and functioning at 6 months in Veterans receiving ACT. Changes in anxiety symptoms, depressive symptoms, pain acceptance and engagement in values-based behavior from baseline to 6 weeks and 3 months will be used as potential mediators for changes in pain and functioning at 6 months.

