For variables in the primary aim (pain severity and functioning), efficacy of ACT compared to AC at 6 weeks, 3 months and 6 months will be tested using linear mixed model analysis for repeated measures. The fixed effect in the model will include intervention group, time, and intervention*time interaction effect. The model will also include site, workshop (cluster) within intervention, and subject as random effects. Test of mean contrast will be used to compare between treatment group means and mean change from baseline to 6 weeks, 3 and 6-months post-TKA between ACT and AC. P-values will be adjusted using Bonferroni's method to account for the number of tests performed. The efficacy of ACT versus AC will be expressed as the group mean difference with a 95% confidence interval (CI), using the SAS STAT (14.1) MIXED procedure.

For the secondary aim (A), efficacy of ACT compared to AC on anxiety symptoms, depressive symptoms, pain acceptance, and engagement in values-based behavior will be compared using linear mixed model for repeated measures. Intervention group mean differences will be estimated and tested as described in the analysis for the Aim1 variables.

For the primary and secondary aim analyses, it is expected that randomization will lessen the need for covariate or moderator adjusted analyses. However, if any demographic, baseline, time from workshop to surgery, or perioperative variables (i.e. perioperative anesthesia/analgesic, postoperative complications, postop day 1 pain and function, etc.) are found to differ between intervention groups, the model will be expanded to include these variables as covariates or effect moderators to estimate and test intervention group mean differences, or odds ratio, controlling for these variables.

In addition to the analyses described above for the primary & secondary outcome measures, similar linear mixed model analyses that include all randomized subjects will be performed. This secondary analysis will include surgery status in the model to contrast the impact of the intervention on those with and without surgery.

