For the exploratory aim, frequencies for each pharmacologic and non-pharmacologic pain management strategy will be calculated to describe the types of strategies reported at each visit. Patterns (from baseline to 6 months) and trends (i.e. changes over the 4 year data collection period) will be examined. Helpfulness ratings will be averaged using means and standard deviations or medians and interquartile ranges for each strategy to provide insights on strategies at-risk Veterans find helpful. Differences in types and helpfulness of pain management strategies by treatment group will be explored.

Sample Size

Sample size was estimated using KOOS-Activities of Daily Living Subscale (the primary outcome requiring the largest sample size). According to the literature, a change of 8 points or more represents a clinically significant improvement.⁸⁵ Therefore, assuming an average of 6 participants per workshop (cluster), with an ICC of 0.06 and a standard deviation of 18, a sample size of 300 Veterans (n=150 per treatment group) will be needed to detect a clinically

significant difference of 8 at a 0.0167 significance level (adjusted for testing at 3 time points) with 0.80 power. Assuming 20% will have surgery cancelled/postponed due to health issues and 10% will drop out after randomization (17% and 10%, respectively, was observed in our R34 study), we plan to enroll 430 Veterans to ensure that we will have $n=150$ per treatment group for the primary aim analyses. Veterans who do not have surgery after randomization will be followed over a similar timeframe and will be included in the secondary analyses.

Recruitment, Consent and Enrollment

Summary of recruitment and consent process, in-person

Identifying Patients

In order to increase awareness of the study, flyers describing the study will be posted in the orthopedics clinic and copies will be made available for patients to take. The study's Research Assistant (RA) will use Vista to identify all patients scheduled in the VAMC Orthopedics Clinic for a knee pain consultation. The RA will then review these patients' medical records to determine if they speak English with adequate competence AND do not have a diagnosis of dementia, bipolar or psychotic disorder, or history of brain injury. They will also review prior orthopedic notes to gauge readiness for surgery.

Approaching Patients

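### Sizing allows for three visits only, but the Bonferroni family for three primary outcomes at three visits is undefined: neither reading gives both 0.80 power and 5% error over the primary aim

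*Combined protocol and SAP*

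**What the plan says.** **Outcomes.** The Primary Aim (Précis, Objectives) names BPI Pain Severity for pain, and says that "level of functioning will be measured using the KOOS Activities of Daily Living and Quality Of Life Subscales". The KOOS entry under Data Collection Instruments confirms that both subscales are primary function measures. That makes three primary outcomes.

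**Visits.** The Data Analysis section tests the primary-aim variables at 6 weeks, 3 months and 6 months. Study Design calls 6 months the primary endpoint only for mediator effects. No single outcome or visit is named for the efficacy test, and no testing order is given.

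**Contrasts.** The mixed-model contrasts are to "compare between treatment group means and mean change from baseline to 6 weeks, 3 and 6-months post-TKA between ACT and AC".

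**Multiplicity.** P-values are adjusted by the Bonferroni "method to account for the number of tests performed". The tests to be counted are not listed. Effects are reported with 95% confidence intervals, which are not said to be adjusted or unadjusted.

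**Sizing.** The Sample Size section uses KOOS-ADL, described as the primary outcome that needs the most participants. It takes 8 points as the target because "a change of 8 points or more represents a clinically significant improvement", and proceeds "assuming an average of 6 participants per workshop (cluster), with an ICC of 0.06 and a standard deviation of 18". It arrives at 150 per arm for a "significant difference of 8 at a 0.0167 significance level (adjusted for testing at 3 time points) with 0.80 power".

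**The concern.** The sample size divides 0.05 by three, for visits. The primary aim contains 3 outcomes x 3 visits = 9 between-arm tests. The analysis text introduces the Bonferroni rule in a paragraph about all the primary-aim variables, so a reader may count three tests or nine. The two counts lead to different trials. One has less power than stated; the other has no error control across its three primary outcomes.

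With the family open, the threshold for a positive result (0.0167 or 0.0056) could be settled after the results are seen, and that choice could decide whether the primary aim is met.

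**Working it through.** **Inputs** (Sample Size section): difference d = 8, SD = 18, ICC = 0.06, m = 6 per workshop, n = 150 per arm, hence 25 workshops per arm. Sidedness is not stated. I assume two-sided tests, because 95% intervals are reported and a one-sided calculation gives about 116 per arm, which does not fit 150.

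**Formulas**
- Design effect: 1 + (6 - 1) x 0.06 = 1.30.
- Standardised effect: 8 / (18 x sqrt(2 x 1.30 / 150)) = 3.376.
- Normal power: Phi(3.376 - z), where z is the two-sided critical value.
- Cluster t power: noncentral t with 2 x (25 - 1) = 48 df and noncentrality 3.376.

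**Step 1: the plan's own figure.** At alpha 0.0167 the normal critical value is 2.393, so power is Phi(0.983) = 0.84. The cluster t gives 0.81, and 25 workshops of 6 per arm is the smallest whole number reaching 0.80. The stated 150 therefore reproduces exactly on the cluster t. The normal formula gives 2 x (18/8)^2 x (2.393 + 0.842)^2 x 1.30 = 138 per arm.

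**Step 2: KOOS-ADL power by family size, 150 per arm**

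| Bonferroni family | alpha per test | Power, cluster t | Power, normal |
|---|---|---|---|
| 3 visits within one outcome | 0.0167 | 0.81 | 0.84 |
| 9 primary-aim tests | 0.0056 | 0.68 | 0.73 |

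At 0.0056, 0.80 power would need 172 per arm (normal) or 186 (cluster t).

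**Step 3: familywise error if only visits are corrected.** I simulated nine correlated normal test statistics under no effect, each tested at 0.05/3. The documents give no correlations, so these are assumptions: 0.6 between visits, and a range between outcomes.

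| Assumed between-outcome correlation | Familywise error |
|---|---|
| 0 | 12.1% |
| 0.5 | 10.9% |
| 0.7 | 9.6% |
| 0.9 | about 7% |

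The Bonferroni bound is 3 x 5% = 15%. Under the same assumptions, Bonferroni over all nine tests stays below 5% throughout.

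**Step 4: intervals.** If the 95% intervals are unadjusted, a result with |z| between 1.96 and 2.77 has an interval excluding zero while its nine-test Bonferroni p-value exceeds 0.05. With a three-test family the range is 1.96 to 2.39.

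**The case against.** The strongest reply is that the analysis and sizing texts agree. The plan's only explicit count is three, for time points. Bonferroni over the three visits within each outcome's model is a consistent reading, and it delivers the stated power. This stands. A reader might infer that the rule counts all primary-aim tests and that the 0.80 is therefore simply wrong; the text does not say so, and no figure in the Sample Size section is miscalculated. The reply does not close the point, because on that reading nothing controls error across three outcomes that are all called primary.

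A reader might also count 18 tests, because group means and mean changes are both mentioned. That wording can equally describe one comparison per visit, and the Primary Aim is stated as change from baseline only. The resulting alpha of 0.0028, with power 0.59 to 0.65, is a worst case and not a finding.

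The size of the power loss is also open to challenge. The plan does not say whether SD 18 refers to raw or change scores. If it is a raw-score SD, the change-score SD is 18 x sqrt(2(1 - r)), where r is the baseline to follow-up correlation. Assuming r of 0.4, 0.5, 0.6 and 0.7, with the same ICC, cluster t power at 0.0056 is 0.57, 0.68, 0.80 and 0.92. So a shortfall under nine tests is not certain. The plan gives no r and claims no such gain.

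The error range likewise rests on assumed correlations. Its upper end needs pain, daily function and knee quality of life to be uncorrelated, which is implausible.

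Finally, unadjusted intervals beside adjusted p-values are not an error in themselves. The gap is that the plan does not say which they are.

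**Conclusion.** The concern holds as a mismatch between an undefined family and a sizing alpha that allows for visits only. On the plan's inputs:

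- Family of nine tests: error over the primary aim is controlled at 5%, and KOOS-ADL power is about 0.68 to 0.73 instead of 0.80.
- Family of three visits per outcome: power is 0.81 to 0.84, and familywise error over the three outcomes is about 7% to 12%.

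Neither reading gives both stated power and 5% error. This rests on two-sided tests, equal workshops of six, SD 18 as the SD of the analysed contrast, no gain from baseline or repeated measures, and, for the error range, between-visit correlation 0.6 and between-outcome correlation from 0.9 down to 0. The power figures are per test and for KOOS-ADL only, since the documents give no SD or target difference for BPI severity or KOOS-QoL.

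**What to change.** Before unblinding, write the primary family into the Data Analysis section, with one between-arm contrast per outcome and visit. Then choose one of two routes:

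1. **Keep three primary outcomes.** Replace Bonferroni with Holm over the nine tests; it gives the same familywise control and is never less powerful. Restate KOOS-ADL per-test power as about 0.68 to 0.73 at Holm's first step (alpha 0.0056, 150 per arm). Note that this takes SD 18 as the SD of the analysed contrast and claims no baseline or repeated-measures gain.
2. **Name one primary outcome for the confirmatory test.** Keep 0.0167 over its three visits, and declare the other two outcomes secondary or test them in a stated order. If KOOS-ADL is named, the stated 0.80 stands.

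Under either route, align the Sample Size wording with the chosen family and state whether the 95% intervals are multiplicity-adjusted.

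The change is to wording only. Route 1 needs no extra enrolment provided the sponsor accepts the lower stated power; route 2 keeps the power but narrows the primary claim.

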Participants will be allowed to take breaks and lunch will be provided (at in-person workshops only). Participants will be sent an invitation approximately 2 weeks before their scheduled workshop, a reminder letter 1 week before the workshop and, if they have consented to participate in the Department of Veterans Affairs' Annie mobile Short Message Service (SMS) text messaging, a short text message reminding them of the workshop. They will also receive a reminder call and message one day before the workshop. If participating in an online Zoom workshop, the participant will be sent instructions for using Zoom and a link to join the workshop via their own computer/tablet or they will be sent an iPad via registered mail with the link bookmarked. A research team member will also call the participant the day before to review the instructions for connecting to the virtual workshop. If a participant fails to attend their scheduled workshop, they will be contacted to reschedule. If they repeatedly fail to attend a workshop and do not respond to attempts to reschedule, a letter will be sent requesting they contact the study.

ACT

The ACT workshop will cover the following topics 1) Acceptance and Mindfulness Training emphasizing new ways of managing troubling thoughts, feelings, and physical sensations (e.g., learning how to recognize, and develop cognitive distance from, unhelpful thoughts such as "I can't take this pain anymore" or "This is unfair") and learning how to willingly face experiences that cannot be changed; and 2) Behavioral Change Training involving a) teaching patients how to recognize ineffective patterns of behavior and habits, b) exploring and setting life goals and goals related to mental and physical health, and c) promoting effective and committed actions to achieve these goals despite the urge to do otherwise. Participants in the ACT workshop will receive two manuals and a deck of therapy cards. At the end of the ACT workshops, ACT participants will be asked to document a goal that will be reviewed at the booster session.

AC

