This study will use a cluster randomization approach where the unit of randomization will be the workshops. Randomization will occur right before each workshop so that all participants attending that workshop will be randomized to that intervention (i.e. ACT vs. AC). Statistician [name] will generate the randomization sequence to ensure adequate distribution of the two interventions over the study period. Randomization will be stratified by site (i.e. Iowa City versus Houston). The randomization sequence will be maintained by the Statistician in a password protected file. This file will be used to generate concealed envelopes maintained and accessed by a facilitator at each site. Allocation of workshop to intervention group will remain concealed for facilitators until approximately one week before the workshop to allow for the needed preparation. Workshop allocation to intervention group will remain concealed for all other study personnel and participants until the beginning of the workshop when all invited participants have arrived. Those in attendance will receive the assigned intervention. This allocation approach will eliminate pre-treatment withdrawals, minimize the potential for experimenter and participant bias by protecting the randomization sequence in a central location, maintain concealment of treatment allocation until the last possible moment, and keep the participants and outcome assessors blinded to treatment.

Virtual Workshops

The randomization scheme for BCM should be used for all virtual workshops.

Blinding

This is a double-blind study. Participants are blinded to which treatment is the treatment of interest and outcome assessors will be blinded to which treatment participants receive. The treatment allocators (i.e. project coordinators) and the workshop facilitators will not be blinded so they can be available throughout the study to answer questions regarding treatment. It is essential for them to know which group the participant is in, in case they need to troubleshoot the treatment.

Participants will complete the Workshop Usefulness Survey (Workshop Question 6wk) in REDCap at the end of their 6-week assessments and the Participant Blinding Question in REDCap at the end of their 6-month assessment. Assessors will complete the Assessor Blinding Question (Workshop Question 6mo) in REDCap at the end of each participants' 6-month assessment.

Post-Op Evaluations

6 Weeks, 3 Months and 6 Months Post-Op Surveys

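### Facilitators learn a workshop's arm about a week ahead, while the attendee list that defines the arm is still open and no rule closes it first

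*Combined protocol and SAP*

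**What the plan says.** The Randomization section makes the workshop the unit: "This study will use a cluster randomization approach where the unit of randomization will be the workshops". Arm membership follows from presence on the day: "Those in attendance will receive the assigned intervention".

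The same section describes timing in two ways. One sentence reads: "Randomization will occur right before each workshop so that all participants attending that workshop will be randomized to that intervention". A later one keeps allocation "concealed for facilitators until approximately one week before the workshop", so that they can prepare. The envelopes are held and accessed by a facilitator at each site. Everyone else, staff and participants alike, is to remain concealed until the session starts with the invitees present. The section presents this as concealment to the last possible moment and as a way to remove withdrawals before treatment.

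The Blinding section adds a second unblinded role: "The treatment allocators (i.e. project coordinators) and the workshop facilitators will not be blinded". It does not say when coordinators learn the arm of a given workshop.

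Study Interventions sets the pre-workshop contacts: an invitation about two weeks ahead, a reminder letter one week ahead, and a call and message the day before. For absences it says: "If a participant fails to attend their scheduled workshop, they will be contacted to reschedule". Groups may hold 3 to 10 Veterans.

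**The concern.** When clusters are randomized and individuals join by turning up, the comparison is protected only if the list of joiners is settled before anyone able to influence it knows the arm. Here some staff know the arm for about a week while the list can still change. A facilitator aware of the arm could, without any ill intent, encourage one person to come and suggest a later date to another.

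Such a change would leave little trace. Someone who drops off the list in that week is not a randomized withdrawal, because randomization is defined by attendance. The Data Analysis section's primary set is randomized subjects who had surgery, and its secondary set is all randomized subjects. Neither contains rostered non-attenders. The planned comparison of drop-outs between arms covers study participants who leave, and nothing asks for rostered-but-absent counts by arm.

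**Working it through.** **Step 1. Put the timeline together** (Study Interventions, Randomization, and the summary of post-consent screening and pre-randomization assessment).

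| Time | Event | Who knows the arm, per the text |
|---|---|---|
| Before scheduling | Eligibility and baseline surveys completed | Statistician (holds the sequence) |
| About 2 weeks before | Invitation | Statistician |
| About 1 week before | Reminder letter; arm disclosed to facilitators | Plus facilitators |
| 1 day before | Reminder call and message; extra call for Zoom users | Plus facilitators |
| Workshop start | Those present receive the arm | Everyone present |
| Afterwards | Absentees contacted to reschedule | The next workshop is sealed unless its own week has begun |

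The invited list is normally formed while the arm is concealed. Attendance and rescheduling are not fully covered, because both can be settled after facilitators know.

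**Step 2. Look for a rule that closes the gap.** No section freezes the roster before the envelope is opened. None bars facilitators or coordinators from reminders or rescheduling. The Zoom set-up call is assigned only to a research team member, and the general reminder call to nobody in particular. The Randomization and Blinding sections do not agree on who allocates.

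**Step 3. The plan's own figure.** The point does not affect the sample size, but the planned precision gives a scale.

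- Inputs (Sample Size section): difference 8, SD 18, alpha 0.0167 (two-sided assumed), power 0.80, 6 per workshop, ICC 0.06.
- Without clustering: 2 × [18 × (z for 0.0167 two-sided + z for 0.80) / 8]² = 105.95, so 106 per arm.
- Design effect: 1 + (6 − 1) × 0.06 = 1.3. Then 105.95 × 1.3 = 137.7, so 138 per arm.
- With a noncentral t on 2(k − 1) degrees of freedom for k workshops per arm, power is 0.791 at k = 24 (144 per arm) and 0.811 at k = 25 (150 per arm). This reproduces the stated 150.
- Enrolment: 300 / (1 − 0.30) = 428.6, so 429, consistent with 430.
- Standard error of the difference: 18 × √(2 × 1.3 / 150) = 2.37 KOOS-ADL points.

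**Step 4. Illustration only.** Suppose a share f of one arm's attendees is replaced, through steering, by people whose outcome differs by D standard deviations. Then bias = f × D × 18. Both f and D are assumptions; the documents give neither. Type I error uses the normal approximation with SE 2.37.

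| f | D | Bias (points) | Type I error (nominal 0.0167) |
|---|---|---|---|
| 5% | 0.25 | 0.05 × 0.25 × 18 = 0.23 | 0.017 |
| 10% | 0.5 | 0.10 × 0.5 × 18 = 0.9 | 0.025 |
| 20% | 0.5 | 0.20 × 0.5 × 18 = 1.8 | 0.052 |
| 20% | 1.0 | 0.20 × 1.0 × 18 = 3.6 | 0.19 |

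Only steered changes count towards f. Participants do not know the arm, so ordinary cancellations and absences do not depend on it.

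**The case against.** The case against is substantial, and most of it stands.

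- **Invitations come first.** They go out about a week before facilitators learn the arm, and no section describes late additions or swaps.
- **Concealment of others is explicit.** A reader might infer that staff in general know the arm early, or that the unblinded staff are the ones in touch with participants. The documents support neither. Research assistants identify, approach, screen and consent patients. The contacts described for facilitators are the workshop and the booster call after surgery. The text does not say who handles reminders and rescheduling, and that silence is not evidence that facilitators do.
- **Coordinators.** A reader might infer that they also know a week ahead. The stated reason for unblinding them is to answer questions and troubleshoot treatment, which fits knowledge gained after allocation.
- **Rescheduling usually meets a sealed envelope.** Assuming even spacing, 430 / 6 is about 72 workshops. Over the four-year data collection period (208 weeks) that is one every 2.9 weeks across both sites; over an assumed three years of enrolment (156 weeks), one every 2.2 weeks. Both exceed the one-week window, though bunched scheduling could change this.
- **The analysis is not helpless.** A reader might infer that no analysis could repair the bias. Baseline measures precede scheduling, the model contrasts change from baseline, and covariates that differ between arms are added. Measured differences can therefore be adjusted for; unmeasured ones cannot.
- **Early disclosure is deliberate.** Facilitators need time to prepare.

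What remains is that concealing others protects the roster only if those others alone control it, and the plan does not say so.

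**Conclusion.** The point holds in a limited form. The procedure leaves a narrow selection route that the stated concealment does not fully close, and selection through that route would not show in the planned reporting. It requires facilitators, or coordinators if they know early, to affect attendance or rescheduling. The documents do not show that this happened or was likely. Eligibility and baseline scores are out of its reach, since both precede scheduling.

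The size of any bias cannot be estimated from the documents. The illustrative 0.23 to 3.6 points, against a target difference of 8, follows entirely from assumed inputs, and nothing in the plan places the trial within that range; no steering at all is also possible. The reason to act is that the safeguard costs little. Separately, the two accounts of when randomization takes place and the two accounts of who allocates are inconsistent as written.

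**What to change.** Amend the protocol and manual as follows.

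1. Close and date-stamp each workshop's roster before its envelope is opened, with no additions or swaps afterwards.
2. Reschedule anyone who cannot attend, or did not attend, only into a workshop whose envelope is still sealed.
3. Have only personnel concealed to allocation handle reminders and rescheduling.
4. Report rostered, attended and rescheduled counts by allocated arm. Enrolled participants already have baseline data and a status in the Tracking Database, so this should be feasible.
5. Reconcile the statement that randomization occurs just before the workshop with disclosure to facilitators about a week earlier. Also reconcile the facilitator as envelope holder with project coordinators as allocators, and state when coordinators learn the arm.

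Facilitators keep their preparation week. The cost is document wording and an occasional empty seat or a wait for the next workshop.
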